3.7 Primary Endpoint

Incidence of major adverse cardiovascular and cerebrovascular events (MACCE) within 24 months after randomization, including all-cause death, recurrent myocardial infarction, stroke, hospitalization for heart failure, outpatient or emergency visits due to worsening heart failure, and repeat revascularization driven by angina pectoris.

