3.8 Secondary Endpoints

1. All-cause death at 24 and 60 months after randomization.
2. Recurrent myocardial infarction at 24 and 60 months after randomization.
3. Stroke at 24 and 60 months after randomization.
4. Hospitalization for heart failure or outpatient/emergency visits due to worsening heart failure at 24 and 60 months after randomization.
5. Repeat revascularization driven by angina pectoris at 24 and 60 months after randomization.
6. Comparison of the difference in left ventricular ejection fraction (LVEF%) measured by echocardiography between the two groups at 24 months after randomization compared to baseline.
7. Comparison of the difference in left ventricular end-systolic diameter (LVIDs) measured by echocardiography between the two groups at 24 months after randomization compared to baseline.
8. Comparison of the difference in left ventricular end-diastolic diameter (LVIDd) measured by echocardiography between the two groups at 24 months after randomization compared to baseline.
9. Comparison of New York Heart Association (NYHA) functional classification between the two groups at 24 months after randomization.
10. Comparison of Kansas City Cardiomyopathy Questionnaire (KCCQ) scores between the two groups at 24 months after randomization.
11. Incidence of adverse events related to fexofenadine.

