3.12 Statistical Methods

| Primary Endpoint | Statistical Methods | Analysis Time Point |
|--|---|--|
| Incidence of major adverse cardiovascular events (MACE, including cardiac death, non-fatal MI, non-fatal stroke, readmission for heart failure, etc.) within 24 months after randomization | Survival analysis, Kaplan-Meier survival curve, Log-rank test | 24th month after randomization |
| Secondary Endpoints | Statistical Methods | Analysis Time Point |
| All-cause death at 24 and 60 months after randomization | Survival analysis, Kaplan-Meier survival curve, Log-rank test | 24th and 60th months after randomization |
| Recurrent myocardial infarction at 24 and 60 months after randomization | Survival analysis, Kaplan-Meier survival curve, Log-rank test | 24th and 60th months after randomization |
| Stroke at 24 and 60 months after randomization | Survival analysis, Kaplan-Meier survival curve, Log-rank test | 24th and 60th months after randomization |
| Hospitalization for heart failure or outpatient/emergency visits due to worsening heart | Survival analysis, Kaplan-Meier survival curve, Log-rank test | 24th and 60th months after randomization |

| | | |
|--|---|--|
| failure at 24 and 60 months after randomization | | |
| Repeat revascularization driven by angina pectoris at 24 and 60 months after randomization | Survival analysis, Kaplan-Meier survival curve, Log-rank test | 24th and 60th months after randomization |
| Difference in left ventricular ejection fraction (LVEF%) measured by echocardiography compared to baseline after randomization | T-test, Wilcoxon rank-sum test | 24th month after randomization |
| Difference in left ventricular end-systolic diameter/body surface area% measured by echocardiography compared to baseline after randomization | T-test, Wilcoxon rank-sum test | 24th month after randomization |
| Difference in left ventricular end-diastolic diameter/body surface area% measured by echocardiography compared to baseline after randomization | T-test, Wilcoxon rank-sum test | 24th month after randomization |
| NYHA functional classification at 12 and 24 months after randomization | Wilcoxon rank-sum test, Chi-square test | 24th month after randomization |
| KCCQ score at 12 and 24 months after randomization | T-test, Wilcoxon rank-sum test | 24th month after randomization |
| Incidence of drug-related adverse events | Chi-square test | 1st, 3rd, 6th, 12th, and 24th months after randomization |

4. Sample Size Calculation

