This study adopts a 1:1 sample size ratio between the experimental group and the control group, with a one-sided α value set at 0.025 and a power (1- β) of 0.8. Based on preliminary study results and relevant clinical data (referring to PARADISE-MI, EMPACT-MI, COLCOT,

FLAVOUR series studies), event rate estimation will be performed using Kaplan-Meier survival analysis. Assuming an event rate of 16.5% in the control group and 13.2% in the experimental group, the expected enrollment period is 2 years. The sample size will be calculated using PASS software. Considering a 10% dropout rate, 1402 patients will need to be enrolled in each group, totaling 2804 patients.

5. Data Management and Confidentiality

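### Kaplan-Meier is named for four component endpoints in which death from other causes is not an event; if such deaths are censored, each arm's incidence is overstated, chiefly at 60 months

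*Protocol*

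**What the plan says.** Section 3.12 of the Protocol gives all the clinical-event endpoints one method. The recurrent MI row reads "Recurrent myocardial infarction at 24 and 60 months after randomization | Survival analysis, Kaplan-Meier survival curve, Log-rank test", the stroke row "Stroke at 24 and 60 months after randomization | Survival analysis, Kaplan-Meier survival curve, Log-rank test" and the revascularization row "Repeat revascularization driven by angina pectoris at 24 and 60 months after randomization | Survival analysis, Kaplan-Meier survival curve, Log-rank test". The row for heart-failure hospitalization or visits names the same methods.

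Section 3.8 lists these events as secondary endpoints in their own right, for example "Recurrent myocardial infarction at 24 and 60 months after randomization". Death is a separate item: "All-cause death at 24 and 60 months after randomization". The primary composite in Section 3.7 does contain death: "including all-cause death, recurrent myocardial infarction, stroke, hospitalization for heart failure".

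The protocol has no censoring rule and names no competing-risk method. It gives no expected rate for any component or for mortality.

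**The concern.** Kaplan-Meier recognises one kind of event. When the endpoint excludes death, a patient who dies event-free normally leaves the risk set as censored, and the estimator treats that patient as still able to have the event later. One minus Kaplan-Meier then estimates the risk in a setting where nobody dies of other causes. It does not estimate the proportion of randomized patients who have the event by the horizon.

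What is at stake is eight planned summaries: four endpoints at two horizons. The excess grows with mortality and does not shrink with sample size. It also differs between arms if the drug changes mortality. This is a method that the protocol names, not a detail it leaves open.

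**Working it through.** **Inputs**
- Composite risk of 16.5% (control) and 13.2% (experimental), from Section 4: "Assuming an event rate of 16.5% in the control group and 13.2% in the experimental group, the expected enrollment period is 2 years". Section 4 states no horizon for these rates. I read them as 24-month risks, the horizon of the primary endpoint.
- The Section 3.7 composite contains all-cause death, so the probability of a component event or death by 24 months cannot exceed the composite risk.
- 1402 patients per group and 10% dropout (Section 4), so about 1402 × 0.9 = 1262 evaluable.
- Component and mortality rates: none in the protocol, so they are varied below.

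**1. The plan's own figure.** No component incidence is stated, so the only figure to reproduce is the sample size. The hazard ratio is ln(0.868)/ln(0.835) = 0.785. With "with a one-sided α value set at 0.025 and a power (1- β) of 0.8", Schoenfeld's formula gives 537 events. With 2 years of uniform accrual, 2 further years for all and every event counted, this means 1259 per group, and 1259/0.9 = 1399 against the stated 1402. This supports reading 16.5% as a 24-month risk. That the match needs events beyond 24 months is a separate matter.

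**2. Direction.** Let A and D be the cumulative cause-specific hazards of the component and of competing death. Then
- 1 − KM = ∫ exp(−A(u)) dA(u)
- cumulative incidence = ∫ exp(−A(u)) exp(−D(u)) dA(u)

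Since exp(−D(u)) ≤ 1, 1 − KM is never below the cumulative incidence, whatever the shape of the hazards. With constant hazards, 1 − KM = 1 − exp(−A) and the cumulative incidence is A/(A+D) × (1 − exp(−(A+D))).

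**3. Upper bound at 24 months, control arm.** H = −ln(1 − 0.165) = 0.1803, and A + D ≤ H. Put A = sH and D = (1−s)H. The excess is 1 − exp(−sH) − 0.165s. It is largest at s = 0.492: 8.49% − 8.12% = 0.37 points. Without constant hazards, the extreme is that every death precedes every component event: (1 − √0.835)² = 0.74 points. In the experimental arm the constant-hazard maximum is 0.23 points.

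**4. Range of assumed shares, control arm.** Death is given 20-40% and the component 20-40% of the composite hazard. For 60 months the hazard is extended: H = 0.1803 × 60/24 = 0.4508 (composite 36.3%).

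| Horizon | Death share | Component share | Death risk | 1 − KM | Cumulative incidence | Excess (points) | Relative |
|---|---|---|---|---|---|---|---|
| 24 m | 20% | 20% | 3.5% | 3.54% | 3.48% | 0.06 | 1.8% |
| 24 m | 40% | 40% | 7.0% | 6.96% | 6.72% | 0.24 | 3.6% |
| 60 m | 20% | 20% | 8.6% | 8.62% | 8.25% | 0.37 | 4.5% |
| 60 m | 20% | 40% | 8.6% | 16.50% | 15.80% | 0.70 | 4.4% |
| 60 m | 40% | 20% | 16.5% | 8.62% | 7.90% | 0.72 | 9.1% |
| 60 m | 40% | 40% | 16.5% | 16.50% | 15.14% | 1.36 | 9.0% |

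(The 16.5% entries at 60 months are a coincidence: 0.4 × 60/24 = 1.) The constant-hazard maximum at 60 months is 2.0 points in the control arm (19.49% against 17.45%) and 1.3 in the experimental arm.

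**5. Against sampling error.** For a 6% component, the standard error of one arm's incidence is √(0.06 × 0.94/1262) = 0.67 points. That of a between-arm difference is √(2 × 0.06 × 0.94/1262) = 0.95 points. The 24-month excess lies below both.

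**6. Risk difference.** With a death share of 30% and a component share of 40% in both arms, the 60-month difference is 16.50 − 13.20 = 3.30 points by 1 − KM and 15.46 − 12.54 = 2.92 by cumulative incidence, so it is too high. With A = 0.09 against 0.07 and D = 0.16 against 0.25 (control against drug), it is 8.61 − 6.76 = 1.85 by 1 − KM and 7.96 − 5.99 = 1.97 by cumulative incidence, so it is too low.

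**The case against.** The strongest reply is that the protocol nowhere says death is censored, and that censoring rules are commonly set in the statistical analysis plan, which is not shown. That is right as far as it goes, and it is why the point is conditional. It does not dispose of the point. The named estimator, applied in the ordinary way, censors these deaths. The alternatives are to count death as an event, which changes the endpoint, or to keep deceased patients in the risk set, which in effect gives a cumulative incidence. The protocol states neither.

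Second, items 2 to 5 of Section 3.8 give only an event and time points. They do not name a proportion as the target, so a reader who infers a direct contradiction between 3.8 and 3.12 goes beyond the text. The bias arises when the curve is read as the incidence at 24 or 60 months.

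Third, a reader might take all four endpoints to be non-fatal. Section 3.8 and the secondary rows of Section 3.12 do not use that word for recurrent MI or stroke. If fatal MI and fatal stroke count, only other deaths compete there, and the excess for those two endpoints is smaller than all-cause mortality would suggest.

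Fourth, the effect is small at 24 months. This stands. Larger figures can be produced: with 20% mortality, a true 8.0% would appear as 8.9%. But at 60 months this needs death to carry about half of the extended composite hazard (0.223/0.451), and nothing in the protocol supports that.

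**Conclusion.** The point holds conditionally and for secondary reporting only. If deaths from other causes are censored, 1 − KM overstates the incidence of each of the four components in each arm. The direction needs no assumption about rates. The size does. In the control arm it is at most about 0.4 points at 24 months, given constant hazards and 16.5% read as a 24-month risk. At 60 months it is about 0.4-1.4 points (roughly 4-9% relative), given that the same hazard continues and that death and the component each carry 20-40% of it. The practical case therefore rests on the 60-month analyses.

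Two stronger readings are not supported. One is that the tests or the primary result are compromised. The log-rank test with deaths censored remains valid for the cause-specific hazard, and Kaplan-Meier is right for all-cause death and for the composite as Section 3.7 defines it. (The primary row of Section 3.12 lists cardiac death instead; that mismatch is a separate matter.) The other is that absolute risk differences read from the curves will always be too large. Step 6 of the working shows a case in each direction.

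**What to change.** In the four rows of the Section 3.12 table (recurrent MI, stroke, heart-failure events, angina-driven revascularization):
- Replace the Kaplan-Meier curve with the cumulative incidence function (Aalen-Johansen), taking any death not counted as the endpoint event as the competing event.
- State that fatal MI and fatal stroke count as events of their own endpoint or, if not, that they are competing events.
- Keep the log-rank test and label it a cause-specific comparison.

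Leave Kaplan-Meier in place for all-cause death and for the Section 3.7 composite.

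The cost is a wording change in four rows and minor extra analysis work with standard methods. Deaths are already an endpoint and are recorded at follow-up, so no new data, visits or patients are needed. Reported component rates will be slightly lower.

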3.4 Inclusion Criteria

1. Age \geq 18 years old.
2. Able to verbally confirm understanding of the trial risks, benefits, and treatment options of fexofenadine hydrochloride therapy. He/she or his/her legal representative must provide written informed consent prior to participating in the clinical trial.
3. Acute ST-segment elevation myocardial infarction (STEMI) occurring within 7 days, with diagnostic criteria including:
 - i) Typical clinical symptoms: such as severe crushing pain in the retrosternal or precordial area, usually lasting more than 10-20 minutes, which may radiate to the left upper arm, jaw, neck, back, or shoulders, etc.;
 - ii) Elevated serum cardiac troponin (cTn): at least one measurement above the upper limit of normal (99th percentile of the reference upper limit);
 - iii) ST-segment elevation: new ST-segment elevation at the J point in 2 adjacent leads.
4. Echocardiography indicating segmental wall motion abnormalities.

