3.11.5 Study Content

(1) In-hospital Management

1. Signing of Informed Consent

Each participant or their legal representative must provide informed consent before initiating any study-related procedures.

2. Physical Examination

Complete and document a physical examination, including heart rate, blood pressure, height, and weight.

3. Medical History

Complete a detailed medical history record, including age, gender, NYHA functional status, risk factors (hypertension, smoking, diabetes, etc.), and previous cardiovascular diseases (including myocardial infarction, percutaneous coronary intervention, etc.).

4. Laboratory Examinations

Including routine blood test + C-reactive protein (CRP), liver function, renal function, and routine lipid profile.

5. Electrocardiogram (ECG)

Record a 12-lead ECG at baseline. Document cardiovascular events such as severe arrhythmias occurring during hospitalization.

6. Echocardiography

Complete at least one echocardiographic examination within 3 days after MI.

(2) Post-discharge Follow-up (6th, 12th, 24th, and 60th months)

Laboratory Examinations

Including routine blood test + CRP, liver function, renal function, and routine lipid profile.

Safety and the patient's clinical status will be assessed at each follow-up time point after drug administration.

1. Medical History

Complete a detailed medical history record, supplementing any medical events occurring after enrollment in the trial (including symptoms, potential drug side effects, physical status, recurrence of MI/interventional events/hospitalization, death, etc.), as well as patient medication adherence.

2. Physical Examination

Complete and document a physical examination, including heart rate and blood pressure.

3. Electrocardiogram (ECG)

Routinely record a 12-lead ECG at 6th, 12th, and 24th months after MI.

4. Echocardiography

Complete an echocardiographic examination at 6th, 12th, 24th, and 60th months after MI.

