3.11.6 Data Collection

| Items | Baseline (Before Discharge, ≤3 days) | Follow-up (3 months ±14 days) | Follow-up (6 months ±30 days) | Follow-up (12 months ±30 days) | Follow-up (24 months ±90 days) | Follow-up (60 months ±90 days) |
|--|---|-------------------------------------|-------------------------------------|---|---|---|
| Inclusion/ Exclusion Criteria | O | | | | | |
| Signing of Informed Consent | O | | | | | |
| Medical History Informatio n (Age, gender, height, weight, risk factors, clinical past | O | | | | | |

| | | | | | | |
|--|---|---|---|---|---|---|
| history, NYHA functional status, previous history of heart disease) | | | | | | |
| Medical History Information (Any medical events after enrollment in the trial) | | O | O | O | O | O |
| Medication History* | O | O | O | O | O | O |
| Physical Examination | O | Δ | Δ | Δ | Δ | Δ |
| Vital Signs | O | Δ | Δ | Δ | Δ | Δ |
| Coronary Angiography Images# | O | | | | | |
| Laboratory Examinations (Routine blood test + CRP, liver function, renal | O | | Δ | Δ | Δ | Δ |

| | | | | | | |
|--|---|---|---|---|---|---|
| function, routine lipid profile) | | | | | | |
| 12-lead ECG | O | | Δ | Δ | Δ | Δ |
| Echocardi ographic Results (LVEF%, LVIDd, LVIDs) and Original Images | O | | O | O | O | O |
| NYHA Functional Classificat ion | O | | | | O | O |
| KCCQ Score | | | | | O | O |
| MACE Events | | O | O | O | O | O |
| Drug Distributi on | O | O | O | O | O | |
| Drug- related Adverse Reactions | | O | O | O | O | |
| Medicatio n Adherenc e | | O | O | O | O | |

The timeline for data collection is shown in the table above:

Compulsory coronary angiography or laboratory blood tests during follow-up are prohibited. If a participant experiences an endpoint event, it is recommended to collect ECG and coronary angiography data.

*Medication-related information includes the patient's medication status before admission and after discharge.

O: Mandatory item.

Δ: Non-mandatory but recommended.

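### Minor improvement at almost no cost: the 24-month echo endpoints are tested as unadjusted change scores although a baseline echo is mandatory; ANCOVA would cut the standard error by about 8-19% under stated assumptions

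*Protocol*

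**What the plan says.** The statistical methods table in Protocol section 3.12 gives one row to each echo endpoint. The LVEF row reads "Difference in left ventricular ejection fraction (LVEF%) measured by echocardiography compared to baseline after randomization", and the method beside it is "T-test, Wilcoxon rank-sum test". The end-systolic diameter row reads "Difference in left ventricular end-systolic diameter/body surface area% measured by echocardiography compared to baseline after randomization" with the same method, and the end-diastolic row follows the same pattern. All three are analysed at month 24. No covariate or model is named.

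Section 3.8 defines the systolic diameter endpoint without indexing: "Comparison of the difference in left ventricular end-systolic diameter (LVIDs) measured by echocardiography between the two groups at 24 months after randomization". The diastolic diameter is also unindexed there.

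A baseline echo is built into the trial in three places:

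- Section 3.4 makes an echo finding an eligibility criterion: "Echocardiography indicating segmental wall motion abnormalities".
- Section 3.11.5 requires in-hospital imaging: "Complete at least one echocardiographic examination within 3 days after MI".
- The schedule in section 3.11.6 puts an O against LVEF, LVIDd and LVIDs at baseline and at 6, 12, 24 and 60 months. The key reads "O: Mandatory item".

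**The concern.** A two-sample test on change fixes the coefficient of baseline at one. Unless that happens to be the true regression slope of the 24-month value on baseline, some explainable variation stays in the error term. ANCOVA estimates the slope and removes that variation. Both methods target the same between-group difference under randomisation, so the issue is precision and not bias.

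What is at stake is the width of the confidence intervals for LVEF and ventricular size. By the background section's rationale (less fibrosis, better cardiac function after MI), these are the secondary endpoints closest to the proposed mechanism. The planned test would report them less precisely than the mandatory data allow.

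The diameter rows have a second difficulty. Section 3.8 names the raw diameter and section 3.12 tests the diameter divided by body surface area. These are different variables, and no method can be fixed until one is chosen.

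**Working it through.** **Inputs.** The protocol states no SD, correlation, target difference or power for any echo endpoint, so there is no figure of its own to reproduce. From section 4 come 1402 patients per group, 10% dropout, one-sided alpha 0.025 and 80% power. Assumed here: baseline to 24-month correlation ρ of 0.3, 0.5 and 0.7; a 24-month SD (s1) equal to, 0.8 times or 1.25 times the baseline SD (s0); and an LVEF SD of 10 points for the absolute figures.

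**Formulas (large-sample variance per patient).**

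- Change score: s0² + s1² − 2ρ·s0·s1
- ANCOVA: s1²(1 − ρ²)
- Difference between the two: (s0 − ρ·s1)², which is never negative. At this sample size the cost of estimating one slope is negligible, so ANCOVA does not lose. The gain vanishes only when s0 = ρ·s1.

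**Equal SDs.** The variance ratio, ANCOVA to change, reduces to (1 + ρ)/2.

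| ρ | Variance ratio | SE ratio | SE reduction |
|---|---|---|---|
| 0.3 | 0.65 | 0.806 | 19% |
| 0.5 | 0.75 | 0.866 | 13% |
| 0.7 | 0.85 | 0.922 | 8% |

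The SE ratio does not depend on sample size, alpha or the size of the SD. A simulation of 3000 trials with 1262 per arm gave reductions of 17.7% at ρ = 0.3 and 7.3% at ρ = 0.7, in line with the formula within simulation error.

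**Unequal SDs.**

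| s1/s0 | Variance ratio at ρ = 0.3, 0.5, 0.7 | SE reduction |
|---|---|---|
| 0.8 | 0.502, 0.571, 0.628 | 29%, 24%, 21% |
| 1.25 | 0.784, 0.893, 0.981 | 11%, 6%, 1% |

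Example: with s1 = 1.25·s0 and ρ = 0.7, 1.5625 × 0.51 / (1 + 1.5625 − 1.75) = 0.797/0.8125 = 0.981.

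**Absolute scale for LVEF, equal SDs of 10.** Patients per arm: 1402 × 0.9 = 1261.8, or about 1262. The detectable difference is (1.960 + 0.842) × SD × √(2/1261.8), where SD is 10√(2(1 − ρ)) for change and 10√(1 − ρ²) for ANCOVA.

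| ρ | Detectable, change | Detectable, ANCOVA | Power for 1 point, change | Power for 1 point, ANCOVA |
|---|---|---|---|---|
| 0.3 | 1.32 | 1.06 | 57% | 75% |
| 0.5 | 1.12 | 0.97 | 71% | 83% |
| 0.7 | 0.86 | 0.80 | 90% | 94% |

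The 1-point target is illustrative and is not taken from the protocol.

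**Repeated measures as an alternative.** The 6- and 12-month echoes are also mandatory. Assume 5-20% of survivors lack a 24-month echo, with (baseline to follow-up, follow-up to follow-up) correlations of (0.3, 0.6), (0.5, 0.7) and (0.7, 0.8). A repeated-measures model then has an SE 1.0% to 4.7% below that of ANCOVA.

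**The case against.** The strongest reply is that nothing here is an error. A t-test on change is valid, the endpoints are secondary, and covariate adjustment is often left to a statistical analysis plan, which was not available for this review. The validity point stands and limits the weight of the remark. The appeal to a later plan carries less force: the protocol is not silent but names a specific method, and nothing in it points to baseline adjustment.

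Second, the size rests entirely on assumed values, and 8-19% is narrower than the 1-29% obtained once the SDs may differ. That stands. In absolute terms, with an SD of 10, the detectable difference improves by only 0.26, 0.15 or 0.06 LVEF points.

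Third, 1262 per arm is optimistic. It borrows the dropout allowance made for the event endpoint, while deaths and missed echoes reduce the number further, and section 3.6 permits telephone follow-up. This affects the detectable differences and power but not the SE ratio.

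Fourth, the baseline value may not precede randomisation. Section 3.4 requires only a wall motion finding. Sections 3.11.5 and 3.11.6 time the echo within three days without tying it to randomisation, while section 3.11.4 starts treatment immediately after randomisation. A quantitative echo could therefore follow the first dose. This is a fair caution, but it affects the planned change score equally. It is a reason to define the baseline echo and does not favour the unadjusted test.

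Finally, the indexing conflict is a separate matter of endpoint definition and lends no support to ANCOVA. Agreed; it is raised because it must be settled before the diameter rows can be rewritten. The LVEF change does not depend on it.

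**Conclusion.** The point holds as a minor, optional improvement. Section 3.12 fixes an unadjusted comparison of change for three echo endpoints, although the value needed for adjustment is mandatory in the schedule. Under equal variances and ρ between 0.3 and 0.7, ANCOVA gives an SE 8-19% smaller. Over the wider SD ratios examined, the gain runs from close to nil to 29%. It is not negative in any practical sense at this sample size. Confidence in the direction is high; the size depends on a correlation and SDs that the protocol does not give. The primary endpoint and the trial's sample size are unaffected.

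**What to change.** In section 3.12, replace the method in the LVEF row and the two diameter rows with:

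> ANCOVA of the 24-month value with treatment as factor and the pre-randomisation echo value as covariate; adjusted mean difference with 95% confidence interval. Wilcoxon rank-sum test on change as sensitivity analysis.

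State which echo counts as baseline relative to randomisation, and how patients are handled if their measurements were taken only afterwards. A repeated-measures model using the 6- and 12-month echoes is an acceptable alternative. It keeps survivors without a 24-month echo under missing at random, for the small further gain shown above. Echoes missing because of death need separate handling under any of these models.

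Before rewriting the diameter rows, reconcile sections 3.8 and 3.12 on whether the diameter is indexed.

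**Cost.** For LVEF: wording and a little programming, no new data. For the diameters: the same if the unindexed measure is kept. If month-24 body surface area is the divisor, weight must be recorded at that visit. The follow-up item in section 3.11.5 reads "Complete and document a physical examination, including heart rate and blood pressure" and does not name weight, and section 3.11.6 marks that examination as recommended, not mandatory.

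### The three echocardiographic endpoints are fixed as an unadjusted month-24 change comparison that leaves the mandatory 6- and 12-month scans unused and gives up precision

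*Protocol*

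**What the plan says.** Section 3.8 defines the LVEF endpoint as "LVEF%) measured by echocardiography between the two groups at 24 months after randomization compared to baseline", and the two left ventricular diameters in the same way. In the table of Section 3.12, the LVEF row reads "Difference in left ventricular ejection fraction (LVEF%) measured by echocardiography compared to baseline after randomization". The method for all three endpoints is "T-test, Wilcoxon rank-sum test" and the analysis time point is "24th month after randomization". No covariate and no repeated-measures method is named.

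Section 3.11.5 asks sites to "Complete an echocardiographic examination at 6th, 12th, 24th, and 60th months after MI". The schedule in Section 3.11.6 carries the row "LVEF%, LVIDd, LVIDs) and Original Images | O | | O | O | O | O", which marks baseline and months 6, 12, 24 and 60, and its legend reads "O: Mandatory item". With 2,804 patients, months 6 and 12 yield up to 2 × 2,804 = 5,608 scans. No row of Section 3.12 refers to them.

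Section 4 sizes the trial at 1,402 per arm, with the phrase "Considering a 10% dropout rate". That figure serves the primary endpoint. The protocol gives no effect size, standard deviation, power or missing-scan rate for the echocardiographic endpoints.

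**The concern.** A two-sample test of change at one visit can use only patients scanned at that visit, unless missing values are imputed. It also fixes the coefficient of baseline LVEF at one instead of estimating it. Both cost precision. A patient who leaves after month 12 has already supplied two informative scans, and the named method has no place for them.

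There is also a possible bias. If patients with low LVEF tend to miss month 24, and do so to a different degree in the two arms, the patients left at month 24 are no longer comparable.

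The trial's rationale is less fibrosis and better cardiac function after infarction, so these endpoints are its main mechanistic evidence.

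**Working it through.** There is no echocardiographic figure in the protocol to reproduce, so the size rests on assumptions.

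**Inputs.** From the protocol: n = 1,402 per arm, and 10% dropout used as one plausible missing-scan rate m. Assumed: LVEF SD 10 points at every visit. Two correlation patterns are used, with the 6-to-12-month and 12-to-24-month correlations ρ = 0.6 or 0.75 and the baseline-to-month-24 correlation r = 0.75ρ, that is 0.45 or 0.5625.

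**1. Baseline adjustment.** With equal variances, change has variance 2 − 2r and the baseline-adjusted value 1 − r², in units of SD². The ratio is (1 − r²)/(2 − 2r) = (1 + r)/2.
- r = 0.45: 1.45/2 = 0.725
- r = 0.5625: 1.5625/2 = 0.781

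So adjustment alone removes 22 to 28% of the variance, with or without missing scans.

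**2. Interim scans.** Let P be the partial R² of month-24 LVEF on the 6- and 12-month values given baseline: 0.298 (ρ = 0.6) or 0.441 (ρ = 0.75). Relative to the baseline-adjusted complete-case analysis, the variance is (1 − m)·[P + (1 − P)/(1 − m)] = 1 − mP. The saving is therefore mP:
- m = 0: nothing
- m = 10%: 3.0 to 4.4%
- m = 20%: 6.0 to 8.8%
- m = 30%: about 9 to 13%

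**3. Standard errors at 10% missing.** For the test of change with r = 0.45: 10·√(2 × 1.1/(1,402 × 0.9)) = 0.418.

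| Method | ρ = 0.6 | ρ = 0.75 |
|---|---|---|
| Test of change | 0.418 | 0.372 |
| Baseline-adjusted, month-24 scans only | 0.356 | 0.329 |
| Baseline-adjusted plus 6- and 12-month scans | 0.350 | 0.322 |

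The total saving is 1 − (0.350/0.418)² = 30% or 1 − (0.322/0.372)² = 25%.

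**4. Simulation with other assumptions** (SD 9 to 10, correlations 0.5 to 0.78, about 14% missing). The standard errors were 0.400, 0.364 and 0.353 in the same order. The total saving is 1 − (0.353/0.400)² = 22%. Baseline adjustment gives 1 − (0.364/0.400)² = 17%, and the interim scans a further 1 − (0.353/0.364)² = 6%.

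**5. Bias, same mechanism in both arms.** Missingness depends on 12-month LVEF through one common function. With a true effect of 2 points and ρ = 0.6, missingness was 11.5% and 10.0% in the two arms, and the bias of the test of change was −0.02. Across missing rates of about 10 to 30% and true effects of 0 and 2, it never exceeded 0.04 points.

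**6. Bias, mechanism in one arm only** (deliberately extreme). Bias in LVEF points:

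| Missing | Test of change | Baseline-adjusted, month-24 scans only | With 6- and 12-month scans |
|---|---|---|---|
| 10% | −0.15 to −0.19 | −0.49 to −0.51 | about 0 |
| 20% | −0.29 to −0.35 | −0.91 to −0.96 | about 0 |
| 30% | −0.43 to −0.45 | −1.32 to −1.39 | about 0 |

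Baseline adjustment without the interim scans does worse here than the test of change, for a simple reason. With ρ = 0.6 the baseline-to-12-month correlation is 0.48. The covariance of 12-month LVEF with change is then 0.6 − 0.48 = 0.12, and with the baseline-adjusted residual 0.6 − 0.45 × 0.48 = 0.384, about three times as large.

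**The case against.** The strongest reply is that nothing here is contradictory. Section 3.8 defines a month-24 change and Section 3.12 tests it. A protocol need not analyse every scan it collects, and the interim scans may serve follow-up or description. The analysis set and the handling of missing scans commonly sit in the statistical analysis plan, which is not shown, and a month-24 test is compatible with imputation from the 6- and 12-month scans. The trial is double-blind, which makes arm-specific loss less plausible. These are three of eleven secondary endpoints.

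Much of this stands. That only patients with a month-24 scan are tested is an inference from the named method, not a statement in the protocol. The gain from the interim scans alone is modest. A reader might also infer that, if the drug works, sicker placebo patients will be lost and the remodelling effect understated. The documents do not support that. A drug effect acting through one common mechanism changes the missing rates slightly but leaves negligible bias (step 5). Material bias needs a mechanism that differs by arm, and nothing in the protocol indicates one.

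What does not stand is that the choice has been left open. Section 3.12 names an unadjusted two-sample test, and imputation alone would not turn that into a baseline-adjusted comparison.

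**Conclusion.** The point holds as a loss of precision built into a stated method, with a conditional risk of bias. In the simulation at about 14% missing, the proposed model has roughly 20 to 25% less variance. The formula-based patterns at 10% missing give 25 to 30%. The difference reflects the assumed SDs and correlations, none of which the protocol supplies. Under either set, most of the saving comes from baseline adjustment.

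The interim-scan share in step 2 assumes that every patient without a month-24 scan has both earlier scans, which favours the model. Patients lost before month 6 would reduce it.

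The primary analysis is unaffected. The change is worth making because it is cheap, not because the planned test is invalid.

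**What to change.** In the three echocardiographic rows of Section 3.12:
- Make the analysis a mixed model for repeated measures on months 6, 12 and 24, with arm-by-visit and baseline-by-visit terms and unstructured covariance. The month-24 contrast between arms is the endpoint.
- Keep the two-sample test as a supportive analysis.
- State how patients who die before month 24 are handled. They have no scan to be missing, so this is a choice of estimand that the model does not settle.
- Add a sensitivity analysis for data missing not at random.

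Do not stop at baseline adjustment of the month-24 value. It captures most of the precision but leaves the exposure in step 6.

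The cost is wording in three table rows and the statistical analysis plan, with no new visit, scan or patient. It should be settled before unblinding. The downside is that the model assumes data missing at random and, unless deaths are handled otherwise, estimates a mean as if patients who died had been scanned. The text should say so.
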